## **Adequacy of Protection Against Risks**

### **a. Informed Consent and Assent**

Recruitment and Informed Consent: Several different efforts will be used to recruit potential participants and obtain informed consent from those eligible participants. The research team is responsible for assuring that the UNC IRB has approved the study protocol and has reviewed and approved the informed consent document. Written approval must be obtained from the IRB before the study can begin. Once an individual has been deemed potentially eligible to participate through online and telephone screening, study staff will provide more study details and describe the concept of random assignment, the 36 study conditions, and assessment procedures over the telephone. Individuals who remain interested will receive an email directing them to a unique and secure REDCap link to an online informed consent. After clicking on the link, they will be directed through a series of screens that present the informed consent document. The online informed consent records will be retained, and recruitment of participants will be done by adhering to HIPAA regulations. Accrual reports will list enrolled participants and excluded participants throughout the stages of the research. This routine monitoring allows for early identification and resolution of potential problems during the recruitment phase. The anticipated recruitment duration is 30 months. All key personnel have attended the required courses on human subject protection and HIPAA regulations, and certificates of IRB training completion are on file with the University of North Carolina.

### **b. Protections Against Risk**

Protections against Psychological Risks: As noted above, participants are not required to share this information and can elect not to share sensitive and confidential information with the study. Participants will be encouraged to contact the Principal Investigator if they feel they have incurred any emotional distress as a result of study participation. As this is a voluntary study, a participant is free to exit at any point if discomfort should occur.

Protections against Physical Risks: To ensure medical readiness to begin physical activity, participants will complete a physical activity readiness questionnaire (PAR-Q). The PAR-Q assesses for the following medical conditions: heart problems, chest pains, faintness or dizzy spells, high blood pressure, bone or joint problems such as arthritis that has been or could be aggravated by exercise, prescription medication use, and other medical reasons why exercise would not be advisable. Participants endorsing yes to any items 1-4 on the PAR-Q (experience of heart problems, frequent chest pains, faintness or dizziness, bone or joint problems) will be excluded from the study. We also will monitor any major musculoskeletal problems that develop during the intervention (e.g. broken bones) using a medical events questionnaire at 6 weeks and 3 months and will determine whether these appear related to our study. Participants who develop musculoskeletal problems or other health problems that may affect safe participation will be instructed to stop exercising until the problem resolves and their physician approves resumption of physical activity.

All participants will be advised about safe weight loss practices including dietary change and increasing physical activity at their initial study visit. Participants will be advised to gradually increase their physical activity and to

use walking as a primary form of activity and will be taught that the appropriate rate of weight loss is 1 to 2 pounds per week. In addition, we will carefully monitor changes in weight during our trial. We will collect information at each assessment timepoint on hospitalizations for any psychiatric problem, including depression and eating disorders.

**Protections to Ensure Confidentiality of Participants:** All identifying information collected from participants, including names, email addresses, Internet protocol address numbers, and zip code, will not be directly linked with research data. Instead, each study participant will be assigned a unique ID number. Identifying information will only be collected in order to contact participants. To ensure confidentiality of participants, all surveys and records related to a participant's involvement in this research study will be stored in a locked file cabinet and/or in encrypted files on servers that adhere to the University policy on storage and transmission of sensitive data. Participant identity on these records will be indicated by an ID number, and the information linking these numbers with participant identity will be kept separate from the research records. In addition, all research databases will have password-controlled access, and this will be controlled by critical staff.

During online data collection, questionnaire data will be temporarily stored on the REDCap data server. The REDCap database system provides for secure web-based data entry with the data stored on servers that are maintained by NC TraCS. The data is encrypted during transmission. The servers are located in a secure campus area with all appropriate physical security measures in place. The web and database servers are monitored by the TraCS IT staff, patched frequently, and scanned by a third-party vendor to ensure that they are protected against known vulnerabilities. The scanning application is the standard service for the entire campus. Access is by individual user id and is restricted to the forms and/or functions that the user needs to have. Data will be erased from the REDCap data server after online data collection is completed and the data is transferred to the study database in a secure password protected area.

CareEvolution's MyDataHelps™ mobile app data is securely stored in the HIPAA compliant, Meaningful Use Certified EDC HIEBus™ platform. CareEvolution® platforms comply with the security and privacy controls defined by NIST 800-53 Rev. 4 at the FISMA Moderate baseline. They regularly undergo external formal assessments by a FedRAMP-accredited Third Party Assessment Organization (3PAO). The platform has been granted an Authorization to Operate (ATO) by the National Institutes of Health (NIH) and is FDA Part 11 Compliant ([[contact]](mailto:[contact])). MyDataHelps integrates Fitbit using the Fitbit API.

Fitbit data will be collected using the Fitbit API (Application Programming Interface), which maintains data security by requiring an Access Token when the Fitbit user authorizes our study to access their data. During the consent process, participants will consent for the data from their specific device IDs (Fitbits) to be accessed by our study in order to drive tailored messages. Access to any individual's Fitbit account is protected by user login and password authentication. The risk of breach of confidentiality over the Fitbit website will be partly subject to each individual's comfort in sharing information in their individual profile. To further minimize the risk of breach of confidentiality, all participant activities on the Fitbit website will be voluntary. Consent forms will also clearly communicate the risk of this type of disclosure to participants.

If members of the research team wish to work with the data, they will only receive non-identifiable data. Although unanticipated, if study data need to be transmitted between study staff, encrypted files will be sent. Files will be password protected prior to sending or uploading. Only study staff will have knowledge of file passwords.

**Removal of Patients from Protocol.** Participants will be removed from the protocol should they experience greater than minimal risk as detailed above. Participants will be reminded that their participation is voluntary and that they may withdraw from the study at any time without consequence by contacting the Principal Investigator. In addition, we expect that pregnancies will occur. We will stop all intervention activities for anyone who becomes pregnant.

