**Exclusion Criteria**

1. History of heart attack or stroke within past 6 months
2. Untreated hypertension, hyperlipidemia, or diabetes, unless permission is provided by their health care provider.
3. Health problems which preclude ability to walk for PA
4. Report a heart condition, chest pain during periods of activity or rest, or loss of consciousness on the Physical Activity Readiness Questionnaire (PAR-Q; items 1-4).
5. Report a past diagnosis of or receiving treatment for a DSM-IV-TR eating disorder (anorexia nervosa or bulimia nervosa).
6. Currently pregnant, pregnant within the past 6 months, or planning to become pregnant within the next 6 months.
7. Hospitalization for depression or other psychiatric disorder within the past 12 months. History of psychotic disorder or bipolar disorder.
8. Plans for major surgery (e.g., breast reconstruction) during the study time

---

frame

9. Currently participating in a weight loss, nutrition or physical activity study or program or other study that would interfere with this study.
10. Currently using prescription weight loss medications

Number Of Subjects	72
Study Duration	Each subject's participation will last 4 months.
Study Phases	
Screening	(1) Screening : screening for eligibility and obtaining consent and (2) Baseline assessment
Study Treatment	(3) Intervention : study intervention/experimental treatment.
Follow-Up	(4) Follow-up assessment will occur at 6 weeks and 3 months
Efficacy Evaluations	NA
Pharmacokinetic Evaluations	NA
Safety Evaluations	All medical events and safety data will be assessed at assessment points or when interim events are reported by participants using a standard form used in our ongoing NIH funded trials.
Statistical And Analytic Plan	
The primary objective is to evaluate the feasibility and acceptability of a digital intervention components to increase PA and improve nutrition behaviors among YACS (n=80) at 3 months. Our primary feasibility measures are participation, accrual, and retention rates.
 
The secondary outcome analysis will use mixed effects models to test for differences in MVPA and HEI by intervention components across time (baseline, 6 weeks, and 3 months). Effects will be modeled as component x time interactions with the 3-month outcome as the primary endpoint.

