## **Study Population**

Individuals will be eligible if they meet the following criteria: age  $\geq 18$ -39 years at the time of consent, diagnosed with invasive cancer malignancy between the ages of 15-39 years, diagnosed with invasive malignancy in the last 10 years, with no evidence of progressive disease or second primary cancers, completed active cancer directed therapy (cytotoxic chemotherapy, radiation therapy and/or definitive surgical intervention), except may be receiving “maintenance” therapy to prevent recurrences, have no pre-existing medical condition(s) that preclude adherence to an unsupervised exercise program including cardiovascular disease, congestive heart failure, pulmonary conditions, renal disease, and severe orthopedic conditions, not currently meeting guideline recommendations of 150 MVPA minutes/week (self-report) and guideline recommendations for fruit and vegetable consumption, have the ability to read, write and speak English, have access to the Internet on at least a weekly basis, possess and usage of an Internet e-mail address or willingness to sign up for a free email account (e.g., Gmail), have smartphone with internet access and text messaging plan and be willing to be randomized to any condition.

Exclusion criteria include a history of heart attack or stroke within past 6 months; untreated hypertension, hyperlipidemia, or diabetes, unless permission is provided by their health care provider; health problems which preclude ability to walk for PA; a heart condition, chest pain, or other health problems that influence the ability to follow physical activity recommendations; plans for major surgery (e.g., breast reconstruction) during the study time frame; currently using prescription weight loss medications; currently pregnant, pregnant within the past 6 months, or planning to become pregnant within the next 6 months; report a past diagnosis of or receiving treatment for an eating disorder; hospitalization for depression or another psychiatric disorder in the past 12 months or history of bipolar or other psychotic disorder; currently participating in another weight loss, nutrition, or physical activity study or program; already adherent to the American Cancer Society’s recommendation of exercising  $> 150$  minutes/week of moderate-to-vigorous intensity PA and the American Cancer Society’s recommendation of consuming  $> 5$  servings of fruits and vegetables/day.

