Individuals that reported joint problems, some prescription medications, or current treatment for hypertension or hyperlipidemia will be required to obtain written physician consent to participate (Appendix).

The trial is registered on clinicaltrials.gov (NCT05887401) and was approved by the Institutional Review Board at the University of North Carolina at Chapel Hill on August 18, 2022.

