**Exclusion Criteria:**

1. History of heart attack or stroke within past 6 months
2. Untreated hypertension, hyperlipidemia, or diabetes, unless permission is provided by their health care provider.
3. Health problems which preclude ability to walk for physical activity.
4. Report a diagnosis of psychiatric diseases (schizophrenia, bipolar disorder, depression leading to hospitalization in the past year), drug or alcohol dependency. These conditions may potentially limit intervention adherence.
5. Report a past diagnosis of or treatment for a DSM-IV-TR eating disorder (anorexia nervosa or bulimia nervosa).
6. Plans for major surgery (e.g., breast reconstruction) during the study time frame.
7. Current participation in another PA or weight control program
8. Currently using prescription weight loss medications
9. Currently pregnant, pregnant within the past 6 months, or planning to become pregnant within the next 6 months.

*No exclusion criteria shall be based on race, ethnicity, or gender.*

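### Joint problems exclude a candidate under the safety section's PAR-Q rule but need only physician consent under Study Population, and nothing says which rule prevails

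*Combined protocol and SAP*

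**What the plan says.** Four places in the combined protocol and SAP bear on whether a person with a joint problem may enrol.

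- **Section 5, b. Protections Against Risk.** A yes to any of PAR-Q items 1-4 leads to exclusion. The parenthesis describing those items starts with heart problems and chest pains and closes: "faintness or dizziness, bone or joint problems) will be excluded from the study".
- **Section 2, Study Population, after the exclusion criteria.** "Individuals that reported joint problems, some prescription medications, or current treatment for hypertension or hyperlipidemia will be required to obtain written physician consent". With that consent, the person may take part.
- **Protocol Synopsis, Exclusion Criteria, item 4.** It also cites PAR-Q items 1-4, but gives their content as: "Report a heart condition, chest pain during periods of activity or rest, or loss of consciousness". It has no bone or joint item.
- **Inclusion criteria in the synopsis, Study Population and the Appendix.** Each bars orthopedic conditions only when they are severe, as part of a criterion on conditions that rule out unsupervised exercise.

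The main-text exclusions in Study Population do not cite the PAR-Q. Their nearest wording is "a heart condition, chest pain, or other health problems that influence the ability to follow physical activity recommendations", which does not name bone or joint problems.

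**The concern.** The PAR-Q is the protocol's stated check that a participant is medically ready to start physical activity, and the programme is unsupervised. The same section of the protocol lists joint injury among the risks of increasing activity. If two sections give opposite answers for the same person, two screeners who each follow the protocol faithfully can reach opposite decisions.

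The screening rule also determines who counts as eligible. Section 4 (Primary Endpoint Analysis) defines the participation rate as the share of eligible people who agree to join, and participation is one of three feasibility endpoints that must all be met. A denominator that depends on which section the screener read is not fully defined.

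**Working it through.** No arithmetic applies to the contradiction itself, so the check follows one test case through the text.

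**Test case.** A person reports a joint problem that is not severe, can walk for exercise, meets all other criteria and has a physician willing to consent in writing.

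1. *Inclusion criteria (synopsis, Study Population, Appendix).* The orthopedic bar applies only to severe conditions. The person passes.
2. *Inability to walk (exclusion in the synopsis, Study Population and Appendix).* The person can walk. They pass.
3. *Synopsis exclusion item 4.* Items 1-4 are given as heart condition, chest pain and loss of consciousness. The person reports none of these and passes.
4. *Study Population, consent rule.* A joint problem requires written physician consent, which is obtained. The person is eligible.
5. *Section 5, PAR-Q rule.* Bone or joint problems are among the items that exclude. The person is excluded.

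Steps 4 and 5 give opposite decisions, and no sentence ranks one section above the other.

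**Can the two rules be read in sequence?** Suppose the PAR-Q exclusion is applied first and the consent rule covers only those who remain. Everyone reporting a joint problem on the PAR-Q has then already been turned away, so the mention of joint problems in the consent rule has little or nothing left to act on. The sequence does not reconcile the two.

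**Is the content of items 1-4 fixed elsewhere?** No. The synopsis and Section 5 use the same item range with different content. Section 5 includes bone or joint problems and the synopsis does not.

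**Exact scope.** The consent rule says joint problems, not bone or joint problems, so the direct clash is for joint problems. For a bone problem alone, the clash is between Section 5 and two other places: the narrower description of items 1-4 in the synopsis, and the severe-only inclusion criterion.

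**Effect on the participation rate.** Let E be the number eligible and A the number who agree when the test-case group is counted as eligible. Let that group contain j people, of whom k would agree. The rate is A/E if they are eligible and (A - k)/(E - j) if they are excluded. The two are equal whenever k/j = A/E. The rate therefore moves only if this group agrees at a different rate from everyone else. The documents give neither j nor k.

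**The case against.** The strongest reply is that this may be a slip in one parenthesis. If the synopsis states items 1-4 correctly, joint problems fall outside the exclusion and the consent rule stands alone. That may be so, but the documents do not show it, and the Section 5 sentence is current operative text.

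A second reply is that the PAR-Q item may be narrower than any joint problem, since Section 5 describes the conditions assessed as including "faintness or dizzy spells, high blood pressure, bone or joint problems such as arthritis that has been or could be aggravated by exercise". The exclusion sentence does not repeat that limit, and the consent rule has none. Even on the narrow reading, a person whose joint problem is aggravated by exercise meets both rules.

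A third reply is that the safety stakes are limited, and this stands. Under either rule, someone who reports a joint problem is excluded or needs a physician's written consent. Staff oversight of exercise progression and monitoring of medical events also apply.

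A reader might infer several stronger points that the documents do not support:

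- *Every candidate with a joint problem gets opposite decisions.* This is not so. People with severe conditions, people who cannot walk for exercise and people whose physician withholds consent are kept out either way.
- *Blood pressure is in conflict too.* The list of conditions assessed in Section 5 places high blood pressure ahead of bone or joint problems, but that list is not numbered by item and the exclusion sentence does not mention blood pressure. The hypertension criteria elsewhere are compatible with one another.
- *The Appendix adds to the contradiction.* Its exclusion list includes "drug or alcohol dependency", which the other lists lack, but that has no bearing on the PAR-Q or on joint problems.

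**Conclusion.** The contradiction is real, and it is confined to candidates with a non-severe joint problem who can walk, meet all other criteria and have a consenting physician. For them Section 5 says exclude and Study Population says admit, with no rule of precedence. This rests on the wording alone and needs no numerical assumption.

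Its size cannot be stated. The documents give no frequency of joint problems among candidates, so any headcount would come from outside them. A reader might also infer that the participation rate is biased. That does not follow, because the rate shifts only if these candidates agree at a different rate from others, and nothing in the documents says they do. What is established is inconsistent safety screening and an ambiguous definition of eligible for a primary feasibility endpoint. Consistent screening is the stronger reason to act. The point should be corrected, but it does not undermine the trial's design.

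**What to change.** Reconcile synopsis exclusion item 4, the Study Population exclusions and consent rule in Section 2, and the PAR-Q rule in Section 5 (b. Protections Against Risk) into one list of PAR-Q items. For each item, state whether a yes excludes the person or triggers the physician-consent route. Use that same list in the synopsis, Study Population, the safety section and the screening form. The investigator must decide which rule applies to joint problems; this review does not.

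The participation rate in Section 4 can then refer to eligibility as fixed by that list.

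The cost is protocol wording and a corrected screening form, with no extra participants or procedures. If enrolment has begun, the change goes through an amendment.

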## **Potential Benefits of the Proposed Research to Research Participants and Others**

Intervention participants are expected to improve dietary behaviors, physical activity, ultimately reducing their risk of secondary cancers or cancer recurrence, developing type 2 diabetes, cardiovascular disease, and other chronic diseases. In addition, the results of this study could be used to develop an optimized behavioral intervention to be tested in a similar population and, if effective, could be generalizable to a larger population of young adult cancer survivors. If successful, an automated program that uses a smartphone and other relatively low-cost digital technologies that is optimized for effective treatment components could be disseminated in a larger-scale program, thus benefiting a greater number of young adults cancer survivors.

## **Importance of the Knowledge to be Gained**

There are currently few trials that have used a strictly mobile weight loss intervention that have resulted in clinically significant weight loss in young adults. Should this trial prove effective, it will have great public health relevance, as young adulthood is a critical period for excessive weight gain that is associated with future

This will be one of the first entirely remotely delivered interventions using digital tools to improve physical activity and diet behaviors simultaneously among YACS. This study addresses unmet needs of YACS and their demand for healthy lifestyle programs, uses the ubiquity of smartphones and technology, and employs their preference for remotely delivered health interventions. Further, the study design and digital intervention will enable nationwide recruitment and enhance external validity. This technology-based approach has the potential to deliver a novel intervention with high-reach, at low cost, with the potential for scaling the intervention for future efforts. This approach holds promise at improving body composition, physical function, and quality of life for YACS and thus has the potential for strong public health impact.

